3.0 Inclusion and Exclusion Criteria

Subject Enrollment: All patients will be recruited from the outpatient clinics of Dana-Farber Cancer Institute (both pediatric and adult clinics), the inpatient settings of Boston Children's Hospital and Brigham and Women's Hospital, the inpatient or outpatient clinics of Massachusetts General Hospital, or virtually. Eligible study participants will give written consent to the primary investigator or study staff member before initiation of study procedures if recruited in-person. If participants are enrolled and complete study procedures virtually, they will provide verbal consent before initiating study procedures.

If in-person visits cannot be conducted, eligible participants will be still be mailed a prenotice letter (Appendix B) that offers the chance for participants to opt-out or opt-in via email or phone call. After one week, we will call participants we have not heard from and ask if they would consider participating.

Patient Eligibility criteria will include patients who are:

- i) Diagnosed with advanced cancer (i.e., initial first-line therapy is unsuccessful, marked by progression or relapsed disease)
- ii) Aged between 18-39, which is the legal age for completing an ACP document (e.g., POLST/MOLST);
- iii) Speak English; and
- \underline{iv} Have a caregiver or identified surrogate decision maker who is able to participate.
- iv)v) Treated at Dana-Farber Cancer Institute or Massachusetts General Hospital

Exclusion criteria will include:

- i) A diagnosis of low-grade glioma given the fact that progressive or relapsed low grade may not be clinically characterized as advanced disease and associated poor prognosis.
- ii) Visually impaired (note, hearing impaired is not an exclusion as the video is closed captioned);
- iii) Psychological state not appropriate for ACP discussions as determined by the primary oncologist; and,
- iv) Unable to participate in ACP discussions due to mental incapacity as determined by the Short Portable Mental Status Questionnaire(48).
- ÷

Eligible patient participants will be asked to self-identify one caregiver or surrogate decision-maker that will also be approached for enrollment.

Caregiver eligibility criteria include:

- (i) Speak English;
- (ii) Aged 18 or older,
- (iii) Not visually impaired, and
- (iv) Have an associated patient with advancer cancer who is able to participate.

Only dyads will be enrolled, both patient and caregiver must consent to participation in the study.

4.0 Number and Selection of Subjects

We will conduct a pilot trial in 50 AYA with advanced cancer and their caregivers who will be randomized as dyads to either the video (intervention) or usual care (control). No exclusions by sex will be made.

Given the linguistic limitations of study personnel and materials (English-speaking only) who will be conducting structured interviews, the current study is limited to English-speaking patients only.

5.0 Study-Wide Recruitment Methods

5.1 Training of RAs

Each research assistant (RA) who works on the study will thoroughly review the protocol. Prior to approaching potential participants, the RA will be required to complete a practice consent with the study PI to ensure study procedures are being followed. The RA as well as associated personnel will complete the respective CITI training. In addition, all study staff will be familiar with the DF/HCC Operations and Policies library. In addition to the training mentioned above, new staff will observe a minimum of one consent led by the current RA.

5.2 Subject Recruitment

Participant recruitment: Potential participants will be identified by reviewing the monthly census for AYA with advanced cancer who meet our eligibility criteria from the inpatient and outpatient clinics. Additionally, information about this research study along with the study team's contact information may be included in patient-facing materials (i.e., the young adult program (YAP) newsletter, YAP phone app, fliers in waiting rooms, etc.) to help spread awareness and better identify eligible participants. If an interested patient and or family reaches out to the study team after hearing or reading about our study, we will inform the AYA that we will check to make sure they are eligible and their medical team believes it is appropriate for them to participate. The RA will then confirm the patient's eligibility and still afford the oncologist 72 hours (3 business AYAs) to opt their patient out of the study. Once a potential participant is identified from observing clinic lists, an email will be sent to the oncologist to seek permission to present the study to the patient. The email will detail information about the study, including eligibility and outlined protocol (Appendix A). The oncologist will have 72 hours (3 business days) to opt-out of their patient being approached. Three days will be a sufficient amount of time for providers to reply while not obstructing the progress of our study and is a similar timeframe used in other clinical studies by our research team using an opt-out approach. We may also ask providers if they have any patients that are eligible and would be good candidates for this study as a way to increase our eligible pool. The patient and caregiver will then be mailed a letter outlining the study. The letter will explain the goals of the study and inform the patients that a RA from DFCI will try to approach them at their next clinic visit (Appendix B) or over the phone. This letter includes the email address of the RA for this study and an option for patients to opt-out of being approached or called. All mailings, phone-based approaches, and consent meetings will be conducted by the research team at Dana-Farber.

If in-person enrollment cannot be conducted, eligible participants will still be mailed a pre-notice letter (Appendix B) that offers the chance for participants to opt-out or opt-in via email. After one week, we will call participants we have not heard from using and ask if they would consider participating. If there is no answer, the study team may leave a voicemail without identifying information but that includes a call-back number to contact

a study team member. For interested participants, we will email them a consent form and given the opportunity for them to read the form, ask questions, and consider participating. The research assistant will inform participants of an overview of the study, risks, and benefits, and the RA will also ask if participants wish to go through each section of the consent form together. If there are no further questions and the individual wishes to participate, the RA will ask for verbal consent. Following, the RA will document in the study team's tracking log the date of consent, where it occurred (zoom, phone call), and any important notes. If a dyad enrolls, we will set up a time for the study procedures to be completed via DFCI Zoom, which is HIPPA compliant. The Zoom meetings will be password protected and set up at a time that is convenient for the participant.

The RA will verify the ability of the patient and caregiver to provide consent by explaining the study and having the patient repeat (teach-back) the aims and risks. The clinical staff will not play any role in asking the patient to participate to minimize any coercion. However, the patient and caregiver may ask their clinician for additional details about the study.

Each study participant will receive a \$20.00 gift card after the initial items are completed and a second \$10.00 gift card for completing the follow-up interview 3 months later. Study visits will be coordinated to coincide with regularly scheduled clinical visits or lab draws to reduce out-of-pocket expenses.

6.0 Study Timelines

Participants enrollment in the study will last the course of 3 months with one inperson study visit and one phone-based interview. The study entails a one-time 30-40 minute in-person visit or over Zoom where participants will be randomized to the video aid intervention or information sheet control. Around three months following this initial visit, participants will complete a 5-10 minute follow-up phone-based interview. This follow-up interview will be audio recorded with the participants' knowledge and transcribed for analysis. Participants will have consented to be audio recorded during the informed consent process. All recordings will be de-identified. Given the number of AYA patients typically treated at this institution, we anticipate the study to span 2 years, including 3month data collection tools preparation and survey training, 16 months rolling recruitment, surveying, and 3-month follow-up, 2 months data cleaning, analysis, and manuscript preparation. This timeline will continue to be updated given changes to recruitment/enrollment strategies in the setting of COVID-19.

7.0 **Procedures Involved**

Study design, randomization, intervention, and control arm: We will conduct a randomized controlled trial in 50 AYA with advanced cancer and their caregivers who

will be randomized as dyads to either the video (intervention) or usual care (control) (Figure 1). After enrollment, we will collect the following information from the caregiver: full name, date of birth, zip code, and gender for the purposes of reporting to the NCI and subject level registration.

Figure 1. Data collection time periods for the proposed study.

The interview script for the encounter with participants is provided in Appendix C. Following completion of the pre-intervention questionnaire (Appendix D), the RA will provide a brief explanation of the three types of care (life-prolonging, selective, comfort) and the subjects will be randomized to intervention or usual care. Patients and caregivers in the control group will only receive the verbal description of the three types of care (Appendix C, page 1).

Randomization: We will use a central, computer-generated simple randomization design stratified by race and ethnicity for even recruitment in both arms of the study.

Intervention: The intervention group will use the video decision aid describing the goals-of-care options. Patients and caregivers will review the video using an iPad and will have access to the video via a weblink to review the video on their own (Appendix E for video script, Appendix F for link to video). The development of the video followed a systematic approach, using an iterative process of reviews by oncologists, palliative care clinicians, AYA with advanced cancer and caregivers regarding the design, content, and structure of the video. The video decision aid was developed using the International Patient Decision Aid Standards with content that is intended to be objective and balanced.(49) It is scripted at a fourth-grade level of health literacy in English and has closed captioning (Appendix E). The video is available in English. The video is designed for AYAs with advanced cancer and their caregivers making future decisions. The goal of the decision aid is to use decision science to structure the decision in a way that support's the person's ability to make reasoned decisions by considering: 1). accurate information about each option; 2). the risks and benefits of each alternative; 3). to evaluate each choice within the context of their spiritual and emotional values, and their lifestyles; 4). to make a decision based on trade-offs among options; and, 5). to support ACP discussions with caregivers and clinicians about values, lifestyle, and medical history.

The video is narrated by an AYA who opens with an empathic statement regarding the situation any AYA finds themselves in. Then, there is a transition to contemplating what

the future might hold and decisions about medical care and introducing the concept of ACP. There is acknowledgment that these can often be difficult decisions and that the presence of caregivers often helps. There is an explicit statement regarding values and spiritual beliefs and how that might impact decision making. The video then attempts to translate the preceding conversation into actionable medical orders using the most common three-goal framework that is based on the MOLST paradigm: life-prolonging care (live as long as possible); selective care (live as long and as well as possible); and, and comfort care (live as comfortably as possible). The narrator then begins to describe the salient features of each of the three goals of care, reviewing the risks and benefits of each option, and then discussing the trade-offs among the three options. For each option, visual images illustrate the interventions (CPR, intubation, and hospice care) while discussing risks and benefits. The video was created using filming criteria formulated by this research team and used widely around the country.(50) The video was filmed without the use of prompts or stage directions (i.e., no actors; all real clinicians, patients, and caregivers) to convey a candid realism in the style known as cinema verite. (50, 51) At the conclusion of the video, each patient and caregiver in the intervention arm will receive a code to access the video at home and a printout version of the checklist (Appendix G)

Control arm: Patients and caregivers in the control group will only receive the verbal description of the three types of care (Appendix C, page 1).

Study staff will pull data from the patient's emergency medical record as a part of the baseline data collection and again after 3-month follow-up to determine ACP documentation.

8.0 Data Management and Confidentiality

8.0 The patient information sent by Massachusetts General Hospital (MGH) to Dana-Farber will be sent through a send secure email. No PHI will be sent to MGH.

Data elements of survey questionnaire: We are interested in studying the influence of the video compared to enhanced usual care on medical care options and concordance rate with 50 AYA with advanced cancer and their caregivers. To assess study outcomes, data will be collected, to the extent possible, using validated tools. Table 1 outlines the data elements that will be obtained from both patients and caregivers. The audio recording and de-identified transcripts will be stored in a stored location on a secured network only accessible to the study team. The audio recording and de-identified transcripts will be stored in a stored location on a secured network only accessible to the study team.

Sociodemographics: Data on sociodemographics will include age, gender, race, ethnicity, health insurance, education, marital status, religion, and religious attendance. (Appendix D, page 1-2, questions 1-8).

Preferences: Patients and caregivers will be asked for their goals-of-care preference (lifeprolonging, selective, comfort, or Unsure), CPR preference (Yes, No, or Unsure), and ventilatory support (Yes, No, or Unsure) at baseline, and then again immediately after watching the video or reviewing the informational sheet (Appendix D, page 4, question 1-3; Appendix H, page 1, question 1-3) and then we will contact all patients after 3 months by telephone to ask for their preferences.(11, 13, 20) (Appendix I, page 2-3, question 1-3). We will also have an open-ended question for those patients who change their preferences from the initial post-video or control survey ("Can you explain why you have changed your preference from the one stated three months ago?"). AYAs and caregiver concordance of preferences (i.e., the same preference) is our primary outcome.

Knowledge: We will ask five true/false questions and one multiple choice question regarding knowledge of goals-of-care options which were used and validated in our previous studies.(11, 13, 20) (Appendix D, page 6; Appendix H, page 3).

Decisional conflict: We will measure decisional conflict, which attempts to measure uncertainty regarding decision making.(52) The Decision Conflict Scale is a wellvalidated and commonly used tool, we will use the 4-item SURE scale for ease of use and to reduce burden on the participant.(52) (Appendix D, bottom of page 4, questions 1-4; Appendix H, bottom of page 1, questions 1-4).

ACP engagement: We will ask four validated questions to patients only regarding ACP engagement (How ready are you to talk to your caregiver? To your doctor? To appoint a surrogate? To sign an ACP document?).(54) (Appendix D, page 4; Appendix H, page 2).

Comfort with the video: For those patients and caregivers randomized to the video, we will measure acceptability of the decision aid using four questions regarding comfort viewing the video, which we have validated in our prior work.(11, 13, 15, 17, 20-22, 25, 46) (Appendix H, page 4).

Additional outcomes: AYA-reported ACP conversations with caregivers and clinicians will be assessed after three months from baseline survey. Both patients and caregivers will be asked about ACP conversations (Appendix I, bottom of page 3).

Data collection protocol: Based on our prior work, data collection is estimated to take no longer than 40 minutes (10 minutes for informed consent and screening; 10 minutes for baseline assessment; 10 minutes for ACP modality; 10 minutes for immediate follow-up interview) and will be conducted in the outpatient setting. The relatively brief interviewing time (40 minutes) in which the survey is conducted should assure completion of the interview without burdening participants. We do not foresee the additional time to complete the survey to be a barrier to successful recruitment and completion of the protocol.

Participants will be provided written copies of the questions or the questions will be shared with them over zoom (using the "share screen" feature) in order to follow along

during the face-to-face or virtual interviews. The RA will collect baseline data, randomize patients and caregivers as a dyad to either the video or control arm via concealed envelopes, and administer the intervention. After this baseline interview and randomization, the RA will collect the remaining outcomes data regarding preferences, knowledge, and decisional uncertainty from both the patient and caregiver. For those participants randomized to the video intervention, they will also be asked questions regarding the usefulness of the video and their comfort with the video. If patients express interest in creating their own video, RA's may provide an information sheet to guide them through the process (Appendix J). Both patients and caregivers will be contacted at 3 months and assess their preferences and ACP conversations at that time. These phonebased interviews will be conducted independently to reduce influence on the outcome of concordance and will be audio recorded for later analysis.

Table 1: Data Element and Sources									
		SOURCE							
Data Collected	Purpose	Tool	By Whom	From	When	Note			
1. Eligibility screen									
Advanced Cancer	target sub-population identification, covariate		RA, PO	EHR	Daily	HIPAA waiver			
Cognitive Assessment	screening	SPMSQ	RA	interview	Outpatient/Vir tual				
2. Baseline Assessment									
Preferences	2º outcome		RA	interview	Outpatient/Vir tual				
Knowledge	2º outcome		RA	interview	Outpatient/ Virtual				
Randomization followed by video intervention or enhanced usual care									
3. Post-video or informational sheet									
Preferences	2º outcome		RA	interview	Outpatient/ Virtual				
Preference concordance	1º outcome		RA	interview	Outpatient/ Virtual				
Knowledge	2º outcome		RA	interview	Outpatient/ Virtual				
Decisional conflict	2º outcome	DCS	RA	interview	Outpatient/ Virtual				
ACP engagement	2º outcome	ACPE	RA	interview	Outpatient/ Virtual	AYA only			
Comfort with video	2º outcome		RA	interview	Outpatient/ Virtual	Video arm			
4. Follow-up at 3 months									
Preferences	2º outcome		RA	telephone					
ACP conversations	2º outcome		RA	telephone					

KEY: RA: Research Assistant; PO: Primary Oncologist; EHR: Electronic Health Record; SPMSQ: Short Portable Mental Status Questionnaire; DCS: Decisional Conflict Scale; ACPE: Advance Care Planning Engagement Questionnaire.

DATA ANALYSES

Aim 1: H1: AYA with advanced cancer and caregivers randomized to the video will have higher concordance between patients and caregivers (Primary Outcome), and more likely to have higher knowledge, make decisions for less burdensome care (i.e., limited or comfort care, no CPR, no ventilatory support), have lower decisional conflict, and engagement, than those randomized to the control group. Preference concordance between patient and caregiver will be treated as a dichotomized variable and compared between the two study arms using a chi-square test. We will conduct separate analyses for patients and caregivers for secondary outcomes. Knowledge score, decision conflict scale, and ACP engagement will be considered as continuous variables. We will use twosample t-tests or Wilcoxon rank sum tests, whichever more appropriate, to compare the distribution between the two study arms. Chi-square tests will be used to compare the proportion of patients/caregivers choosing less burdensome care between the two study arms. We will explore the effect of patient characteristics (age, sex, etc.) in choosing less invasive care using a logistic regression model. In this study, we will treat sex as selfreported gender and will conduct a sex-based analysis of intervention effects to explore sex as a biological variable. *Power analysis*: Assuming 50% of control arm achieve preference concordance between patients and caregivers, the study will have 80% power to detect a 41% difference (50% vs. 89%) in concordance. Assuming 68% of control patients/caregivers choose non-life prolonging care, the study will have 82% power to detect a 31% difference (68% vs. 99%) in preferences between the two arms. For the continuous outcomes (knowledge, decisional conflict, ACP engagement), the study will have 80% power to detect an effect size of 0.81 with 25 subjects per group.

Aim 2: *H2.* Patients randomized to the video will have more ACP conversations and documentation after 3 months. We will treat conversations and documentation as continuous variables. Assuming 50% of controls achieve ACP conversations/documentation between baseline and three-month follow-up, the study will have 81% power to detect a 27% difference (50% vs. 77%) between the two study arms.

Missing Data: We do not anticipate having substantial amounts of missing data on the initial survey; however, we expect some patients and caregivers to not complete the three-month follow-up surveys. The analyses will initially focus on the study completers (3 months) to estimate the effect of the video intervention on patients who completed the protocol as intended without imposing assumptions about missing data. We will also use the intention-to-treat principle, conducting sensitivity analyses to explore how various assumptions about missing data and differences between completers and non-completers affect the estimated outcomes. If data appear to be missing at random, we will employ multiple imputation methods,(55) maximum likelihood estimate approach with EM algorithm,(56) and mixed-effects modeling(57) that can adequately account for data missing at random. If we find that data are not missing at random, we will employ pattern

mixture modeling to handle incomplete data, and perform sensitivity analysis to assess the impact of missing data

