We have developed a video decision aid for AYAs and their caregivers that reviews treatment options and begins to discuss goals and preferences for their care. The overall objective of this study is to conduct a randomized controlled trial of the video (vs. usual care) in 50 dyads of AYA with advanced cancer and their caregivers. Our hypothesis is that the video better informs patients and caregivers of their options, leads to more ACP conversations, engagement and documentation, and leads to more congruent decision making between AYA and caregivers (primary outcome). Demonstrating the effectiveness of using a video aid in this pilot provides evidence for conducting a larger trial integrating such a video into clinical practice. The

Specific Aims are:

Aim 1: To compare knowledge, preferences and decisional conflict among 50 dyads of AYA with advanced cancer and their caregivers randomly assigned to one of two ACP modalities: 1. The newly created video depicting various goals of care (intervention, 25 dyads), or 2. usual care (control, 25 dyads).

Hypothesis H1a: Patients and caregivers randomized to the video will have higher congruence of preferences between patient and caregiver dyads compared to dyads in the control group (primary outcome). H1b: Those randomized to the video group will have

higher knowledge, fewer preferences for life-prolonging interventions and lower decisional conflict than those randomized to the control group.

Aim 2: To compare ACP conversations between patients with their health care team and caregivers, and ACP documentation between intervention and control dyads. H2: Patients randomized to the video will have more ACP conversations and higher levels of engagement, and more ACP documentation after 3 months.

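### Aim 2 does not say whether documentation already present at entry counts, and gives no role to the baseline documentation status that staff abstract

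*Combined protocol and SAP*

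**What the plan says.** Section 7.0 (Procedures Involved, end of the control-arm text) has staff extract record data "as a part of the baseline data collection and again after 3-month follow-up to determine ACP documentation". So a baseline value will exist for each patient.

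The outcome is described in more than one way:

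- Section 1.0, Aim 2 expects more conversations, higher engagement "and more ACP documentation after 3 months". The trial overview at the end of Section 2.0 likewise speaks of exploring whether conversations and documentation are present at 3 months. Both read most easily as a status at a point in time.
- Data Analyses, Aim 2 repeats the hypothesis ("Patients randomized to the video will have more ACP conversations and documentation after 3 months"), but its power sentence begins "Assuming 50% of controls achieve ACP conversations/documentation between baseline and three-month follow-up", which reads as events within the window.

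The analysis itself is one sentence: "We will treat conversations and documentation as continuous variables". No test, baseline term, change score, definition of new documentation or rule for patients already documented follows. Table 1 does not list documentation.

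For conversations, Section 8.0 (Additional outcomes) says "AYA-reported ACP conversations with caregivers and clinicians will be assessed after three months from baseline survey", and Table 1 lists them only at follow-up.

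Eligibility (Section 3.0) covers patients whose first-line therapy has failed, requires each to "Have a caregiver or identified surrogate decision maker who is able to participate", and does not exclude patients with existing ACP documents.

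**The concern.** H2 is about what the video prompts in the 3 months after viewing. A patient who enters with a document in the record tells us nothing about that if the outcome is simply whether a document is present at 3 months: the patient is a success in either arm. The more such patients there are, the smaller the difference that can be seen. With 25 patients per arm and randomisation stratified only by race and ethnicity, the number already documented can also differ between arms by chance and move the estimate either way.

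Leaving the definition open has a second cost. Any documentation and new documentation can give different results, and the choice between them could be made after the data are seen. The baseline value that would deal with both problems is already being collected.

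**Working it through.** **Inputs.** 25 patients per arm (Section 1.0, Aim 1); 50% vs 77% and 81% power (Data Analyses, Aim 2). Alpha and sidedness are not stated, so two-sided 5% is assumed. No dropout is applied. The share q documented at entry is not in the documents, so a range is shown.

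**The plan's own figure.** The plan states that "the study will have 81% power to detect a 27% difference (50% vs. 77%) between the two study arms". The usual pooled normal formula gives 81.0% with 50 per arm and 51.0% with 25 per arm. The exact distribution of the uncorrected chi-square test gives 81.3% and 54.2%. The 81% is therefore reached only at 50 per arm, although documentation is a per-patient outcome with 25 per arm. That is a separate matter; the working below uses 25 per arm.

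**Case A: earlier documents count as successes, and 50% vs 77% applies to patients undocumented at entry.**

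- Control rate = q + (1 − q) × 0.50
- Video rate = q + (1 − q) × 0.77
- Difference = 0.27 × (1 − q)

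The last column is a simulation of the same setting (200,000 trials per q) using a Mantel-Haenszel test stratified by baseline status.

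| q | Control | Video | Difference (points) | Exact chi-square power, unadjusted | Power, stratified |
|---|---|---|---|---|---|
| 0% | 50.0% | 77.0% | 27.0 | 54% | 54% |
| 10% | 55.0% | 79.3% | 24.3 | 47% | 47% |
| 30% | 65.0% | 83.9% | 18.9 | 35% | 38% |
| 50% | 75.0% | 88.5% | 13.5 | 25% | 28% |

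Stratifying recovers about 0 to 3 points of power. Most of the loss remains, because patients already documented carry no information on this outcome whichever test is used.

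**Case B: 50% vs 77% already describes new events among all randomised patients.** The rates are then the ones the test sees. The difference stays at 27 points and power at 54% for any q.

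**Chance imbalance.** Take q = 30% and independent binomial counts in two arms of 25. The arms then differ by 5 or more already-documented patients in about 16% of trials. In Case A, one more documented patient raises the expected control rate by 0.50/25 = 2 points, or the video rate by 0.23/25 = 0.92 points. A gap of 5 patients therefore moves the expected difference by between 5 × 0.92 = 4.6 and 5 × 2 = 10 points, against an expected 18.9.

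**The case against.** The best defence is that the plan can be read as coherent. The power sentence speaks of what is achieved between baseline and 3 months, and a record pull at each end is the natural way to identify what is new. It also applies 50% to controls as a whole, not to undocumented controls, so Case A discounts rates that may need no discount. This stands as far as the figures go: Case A is an illustration and Case B is a fair reading. It does not settle the definition, because a sample-size assumption is not an outcome definition and the Objectives and overview are worded differently.

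It is also fair that nothing in the documents shows how common prior documentation is. Having a surrogate does not mean that a document exists, and the Background describes ACP in this population as inadequate. Values of q near 50% may be unrealistic. Aim 2 is not the primary outcome, the trial is a pilot, and stratification regains little power.

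A reader might go further in three ways that the documents do not support:

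- **Dilution under either definition.** Counting only new events shrinks the difference only if 50% vs 77% is confined to undocumented patients and those already documented cannot register a new event. The plan says neither, and updated documents are possible.
- **Systematic bias.** Randomisation balances prior documentation on average. What remains is lost sensitivity and chance imbalance.
- **Prior conversations not measured at all.** The baseline questionnaire and the 3-month interview (Appendices D and I) are not in the supplied text. The baseline engagement items described concern readiness, not past conversations, but the 3-month item may already be limited to the period since the visit.

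**Conclusion.** The point holds as a gap in definition and analysis. Baseline documentation is collected but has no stated role in Aim 2, and the documents are inconsistent on whether the outcome is documentation present at 3 months or achieved since baseline.

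Its size cannot be fixed from the documents. It ranges from no dilution (Case B) to a difference of 24.3, 18.9 or 13.5 points instead of 27 at q = 10, 30 or 50% (Case A). These figures rest on an assumed q, a two-sided 5% test, 25 patients per arm without dropout, and a yes/no outcome as in the power sentence, although the analysis sentence calls it continuous.

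The primary outcome is unaffected. The change is still worth making, because the data are already to be collected and a definition is only credible if fixed before results are seen. For conversations, the finding is limited to this: no baseline measure is described in the supplied text.

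**What to change.** In Data Analyses, Aim 2, and matching text in Sections 1.0 and 2.0:

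1. Define the documentation outcome as new or updated ACP documentation dated after randomisation, with the same window for every patient. The second record pull is now tied to a follow-up interview held at around three months, so a common cut-off applied to dated entries would keep the window equal. The exact day is the team's choice.
2. State whether the outcome is yes/no or a count, and compare arms stratified by, or adjusted for, the baseline documentation status already abstracted.
3. Add a supporting analysis in patients undocumented at entry.
4. Confirm that the 3-month conversation item asks about the period since the study visit. A baseline question on past conversations is optional.

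The cost is a few sentences and a date rule for abstraction already planned. The supporting analysis uses fewer patients and will be imprecise. The gain in power is small, about 0 to 3 points when earlier documents count. The main return is protection against chance imbalance and removal of the choice between any and new documentation.
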